The primary efficacy outcome is cotinine-verified 7-day point prevalence abstinence at the end of treatment (Week 12). The primary safety outcome is frequency of treatment-emergent adverse events.

Sample Size and Power

The proposed study is powered on the primary efficacy hypothesis that varenicline will increase abstinence (cotinine verified 7-day point prevalence abstinence), relative to placebo, at the end of treatment (Week 12). While 30-day point prevalence abstinence or continuous abstinence outcomes are ideal, we do not believe an adequately powered study for either approach is feasible within the proposed funding period. There is considerable precedent for using 7-day point prevalence as primary outcome in adolescent smoking cessation pharmacotherapy trials (see **Table 1**). We have recently published a conversion method to estimate continuous abstinence from point prevalence outcomes with a fair degree of confidence (80), and we will track other abstinence outcomes as secondary measures.

The first step towards a sample size analysis is estimating cotinine-confirmed 7-day point prevalence abstinence at end of placebo treatment. We estimate this to be 6.25%, based on the placebo-only end of treatment group abstinence rate in our prior bupropion SR/contingency management smoking cessation study, which was conducted in a nearly identical population to that of the proposed study (15). This estimate is consistent with placebo group end of treatment outcomes in other adolescent smoking cessation trials (e.g., 5% in Moolchan et al., 2005; 5.6% in Muramoto et al., 2007) (17,19). The slightly higher rate in our trial will result in a conservative estimate of the expected effect size (active – placebo), thereby increasing sample size and ensuring sufficient power for hypothesis testing.

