The second step towards a sample size analysis is to estimate the effect of varenicline within adolescent smokers. The only existing adolescent varenicline abstinence data come from our recent pilot trial, in which 26.7% of participants achieved cotinine-confirmed 7-day point prevalence abstinence (27). This results in an anticipated effect size (odds ratio) of 5.5. We recognize that this estimate is based on a small sample size ($n=15$ in the pilot trial varenicline group). However, we do not believe the absolute end of treatment 7-day point prevalence abstinence rates from adult varenicline studies (ranging from 50 to 60%) would be appropriate for sample size estimation in this case, as absolute adolescent abstinence rates (see **Table 1**) are consistently lower than those in adult studies (23,24,81). We do, however, believe that varenicline effect sizes may be comparable across adult and adolescent trials. By this measure, our estimates converge. For example, end of treatment abstinence odds ratios in adults were as follows: 3.8 (23), 4.1 (24), and 9.1 (82). Thus, the sample size estimation is based on anticipated abstinence rates of 6.25% (placebo) and 26.7% (varenicline), for an odds ratio of 5.5. With a type 1 error rate of 5% ($\alpha = 0.05$) and power ($1 - \beta$) of 80%, this would require 51 participants per group using a two-sided Pearson's Chi Square test statistic. However, we still wish to aim even more conservatively, recognizing that (a) this effect size may be an overestimate since the varenicline abstinence rate came from a small sample pilot study, and (b) we must account for attrition for the intent-to-treat analysis. In light of the range of odds ratios in prior adult varenicline studies, we have conservatively targeted detection of an odds ratio of 4.0 for power analysis. Original plans were that we will enroll and randomize **83 participants per group**, for a **total sample size of 166**. This will allow us to detect an odds ratio of 4.0 over the anticipated placebo rate of 6.25%, which would correspond to a varenicline abstinence rate of 21.1%. Due to the higher than expected retention losses within our target population of adolescents and following the current ratio of successfully consented to randomized participants, we estimate that 240 participants will need to be enrolled (consented) to meet our sample size needs.

Efficacy: Primary Analysis

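### Does the 6.25% placebo rate, described as the conservative choice, leave the final 83 per group short of power?

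*Combined protocol and SAP*

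**What the plan says.** The Sample Size and Power text in section C3f works in two stages.

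It first takes the placebo rate as 6.25%, from the team's earlier bupropion SR and contingency management trial, and notes 5% and 5.6% in two other adolescent trials. It presents the higher figure as a safeguard: "The slightly higher rate in our trial will result in a conservative estimate of the expected effect size (active – placebo"). The benefit it claims for this choice is put as "thereby increasing sample size and ensuring sufficient power for hypothesis testing".

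The varenicline rate then comes from the pilot: "Thus, the sample size estimation is based on anticipated abstinence rates of 6.25% (placebo) and 26.7% (varenicline), for an odds ratio of 5.5". At 5% type 1 error and a power "of 80%, this would require 51 participants per group using a two-sided Pearson's Chi Square test statistic".

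The plan does not stop at 51. It gives two reasons for more caution: the pilot was small, and attrition must be allowed for. It then changes the basis of the calculation: "In light of the range of odds ratios in prior adult varenicline studies, we have conservatively targeted detection of an odds ratio of 4.0". The 83 per group is justified in these terms: "This will allow us to detect an odds ratio of 4.0 over the anticipated placebo rate of 6.25"%. The active-arm figure is then read off from that target: "which would correspond to a varenicline abstinence rate of 21.1"%. The 21.1% is therefore an output of the odds ratio and the placebo rate, not an input.

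**The concern.** Whether a higher assumed control rate is cautious depends on what is held constant. With the active rate fixed, raising the placebo rate narrows the difference and increases n. With the odds ratio fixed, and both rates low, raising the placebo rate widens the difference and reduces n.

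The remark about conservatism belongs to the first setting, but the sample size adopted comes from the second, and the text does not limit the remark. A reader could conclude that a true placebo rate of 5% or 5.6% would leave the primary comparison with more than the planned power. At the targeted odds ratio it would leave it with less. What would be at stake is the power for the primary efficacy endpoint, abstinence at Week 12.

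**Working it through.** **Inputs (section C3f).** Two-sided α = 0.05; power 80%; Pearson chi-square; equal groups; placebo rate 6.25%, with 5% and 5.6% as the cited alternatives; varenicline 26.7% in the first stage; odds ratio 4.0 in the second. The plan does not restate α, power or test for the 83 per group. I assume they are unchanged.

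**Formulas.** With p0 the placebo rate, p1 the varenicline rate and p̄ their mean, let A = √[2p̄(1−p̄)] and B = √[p0(1−p0) + p1(1−p1)]. Then

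- n per group = (1.960·A + 0.8416·B)² / (p1−p0)²
- power at n per group = Φ{[(p1−p0)√n − 1.960·A] / B}
- for a fixed odds ratio, p1 = OR·o / (1 + OR·o), where o = p0/(1−p0)

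**The plan's own figures.**

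- First stage, 6.25% against 26.7%: A = 0.5246, B = 0.5043, difference 0.2045. n = (1.0282 + 0.4244)² / 0.2045² = 50.5, so 51, as stated.
- Final stage: o = 0.0625/0.9375 = 0.0667; 4 × 0.0667 = 0.2667; p1 = 0.2667/1.2667 = 21.05%, stated as 21.1%. A = 0.4855, B = 0.4741, difference 0.1480. n = (0.9517 + 0.3990)² / 0.1480² = 83.3. With the rounded 21.1%, n = 82.8, so 83, as stated. Power at 83 per group is 79.9%.

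Neither stage needs a continuity correction or a dropout allowance to reproduce the plan.

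**First stage at the other placebo rates (varenicline fixed at 26.7%).**

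| Placebo | Difference (points) | n per group | Power at 83 per group |
|---|---|---|---|
| 5% | 21.7 | 43.3 → 44 | 97% |
| 5.6% | 21.1 | 46.6 → 47 | 96% |
| 6.25% | 20.45 | 50.5 → 51 | 95% |

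The higher placebo rate does increase n, as the plan says.

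**Final stage at the other placebo rates (odds ratio fixed at 4.0).**

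| Placebo | Varenicline | Difference (points) | n per group | Power at 83 | Exact power at 83 |
|---|---|---|---|---|---|
| 5% | 17.4% | 12.4 | 100.5 → 101 | 72.0% | 74.4% |
| 5.6% | 19.2% | 13.6 | 91.2 → 92 | 76.1% | 78.3% |
| 6.25% | 21.05% | 14.8 | 83.3 → 84 | 79.9% | 81.8% |

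The exact column enumerates both binomial outcomes and applies the uncorrected Pearson test. For example, at 5%: A = 0.4459, B = 0.4372, and power = Φ[(0.1239 × 9.110 − 0.8740)/0.4372] = Φ(0.583) = 72.0%. Here the direction is reversed: 6.25% gives the smallest n of the three. The reversal also appears with continuity-corrected, unpooled and Wald log-odds formulas.

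**Other cases at 83 per group.** At an odds ratio of 5.5, power is 91%, 93% and 95% at 5%, 5.6% and 6.25%. The odds ratio detectable with 80% power is 4.47, 4.22 and 4.01. At an odds ratio of 4.0 and a placebo rate of 10%, power is 92%.

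**The case for a change.** The strongest case for acting is that the sentence is not limited to the first stage. It stands ahead of both calculations and promises sufficient power for the test, which will be run on 83 per group, not 51. The Innovation section gives a similar general assurance that the sample size rests on conservative estimates.

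The remark could be rescued by holding 21.1% fixed, since n then rises with the placebo rate (68, 75 and 83 per group). That does not match the text, which derives 21.1% from the odds ratio and argues that effect sizes, not absolute rates, carry over from adults. Nor is there spare margin: an odds ratio of 4.0 over 6.25% already uses the 80%, and the 83 contains no visible inflation for attrition.

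All of that stands as a comment on the reasoning. It does not amount to a fault in the design. The sentence names its scale, active minus placebo, and is correct for the calculation it introduces. The move to an odds ratio of 4.0 is a second and larger piece of caution, taking n from 51 to 83. The lower powers of 72% and 76% require both an effect at that reduced target and a placebo rate below the plan's own estimate, which comes from a population the plan calls nearly identical. Table 1 also lists placebo rates above 6.25%, up to 28%; at a fixed odds ratio of 4.0 these raise power.

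**Conclusion.** The observation is right but calls for no change. The statement that 6.25% is the cautious choice holds when varenicline is fixed at 26.7% and fails when the odds ratio is fixed at 4.0, which is the basis of the adopted sample size. It is an unqualified line of rationale, not an arithmetic error.

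Its size is modest. At an odds ratio of 4.0, power at the two lower cited rates is about 4 to 8 points below 80% (2 to 6 points by exact calculation). The detectable odds ratio moves from 4.0 to at most 4.5, inside the adult range of 3.8 to 9.1 that the plan cites and below its anticipated 5.5. Power is at least 95% if varenicline reaches 26.7%, and at least 91% at an odds ratio of 5.5.

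Qualifying the sentence would leave the 51, 83 and 21.1%, the enrolment target, the endpoint, the test and the decision rule as they are, and would not affect what the trial can conclude. The figures assume equal allocation, the uncorrected two-sided Pearson test at 5%, and abstinence rates that already count missing participants as non-abstinent, as the primary analysis does.

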The participant age range (14-21) for the proposed study was chosen for multiple reasons. Broad agreement exists to support this range. The Maternal Child Health Bureau defines adolescence as age 11-21, and the Center for Disease Control and Prevention defines it as ages 10-24. NIH defines individuals up to age 21 as children. Given considerable developmental variability from age 10-24, though, a sample inclusive of this range might be overly heterogeneous. Additionally, while many adolescents initiate smoking between ages 10-13, very few smoke at the rate necessary for study inclusion (only 3% of 8th graders smoke daily, and many of those smoke <5 cigarettes per day) (7). Given the potential identification of individuals 22-24 as adults, we opted to exclude this age range as well. We acknowledge that the previous "adult" varenicline clinical trials included participants as young as age 18, but given the studies' mean age of $43 \pm SD 11$, exceedingly few were age 21 or younger, and there have been no published reports on safety, tolerability, and

efficacy within these younger participants. As such, varenicline remains almost completely unstudied among adolescents, even by the broadest age definition.

We do recognize that the developmental context varies considerably even within the narrowed 8-year range of 14-21. To address this, we plan to stratify randomization by age, ensuring that equivalent proportions of those age 14-17 ("younger adolescents") and those age 18-21 ("older adolescents") are represented in varenicline and placebo treatment groups. Given our prior success in recruiting younger adolescents with high school-based clinics and other strategies, we anticipate recruiting similar proportions of younger versus older adolescents, and will adjust strategies if the proportions become skewed. This stratified approach will convey the added opportunity to compare outcomes (in exploratory fashion) between younger and older adolescents.

C3c. Intake and Randomization

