If volunteers complete the informed consent/assent process and are eligible for participation, they will be randomized to double blind varenicline or placebo and will proceed with treatment. In order to avoid accidental bias, we will utilize a stratified urn randomization procedure. We will stratify by the prognostic covariates age (14-17 versus 18-21) and baseline smoking level (<12 versus 12 or more cigarettes per day, based on median baseline smoking in our prior randomized adolescent smoking cessation trial). The age stratification will ensure that both younger and older adolescents will be equally represented in the varenicline and placebo groups. The smoking level stratification will help avoid significantly discrepant baseline smoking between treatment groups. We considered additional stratification variables (e.g., gender, severity of nicotine dependence, presence of other smokers in household, history of attention-deficit/hyperactivity disorder), but, amid concern over excessive division of participants among multiple cells, judged that these could be adequately explored as covariates during efficacy analyses (see Section C3f).

C3d. Treatment

Pharmacological Intervention

The MUSC Investigational Drug Service (IDS) will obtain varenicline 0.5 mg and 1 mg tablets and matched placebo tablets. All tablets will be packaged in blister packs, with individual labels for time/date of each dose (e.g., Tuesday morning October 5th). This date- and time-labeled blister pack method has demonstrated superior participant adherence, compared to traditional packaging, and offers the additional advantage of tracking the exact timing of any missed doses (53-55). The IDS successfully used identical methods for medication/placebo dispensing in our adolescent varenicline pilot study.

If assessment procedures reveal that a participant meets inclusion criteria, the IDS will randomize the participant to varenicline or placebo in double-blind fashion. He/she will be given a 7-day supply of medication to take home. Participants will be given an additional 7-day supply "replacement pack" of medication for use in the event that they cannot make it back for a visit within the 7-day window between visits.

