During the assessment visit, participants will be given adolescent-targeted smoking cessation brochures and briefly counseled on cessation strategies. Participants will be instructed to set a quit date that will occur one week after medication initiation. At weekly visits, participants will be provided with brief (<10 minute) individual skills-based cessation counseling (i.e., enhancing motivation, enlisting social support, recognizing smoking triggers, managing craving/withdrawal/stress), paralleling psychosocial interventions in similarly structured adolescent (17) and adult (23-25) cessation pharmacotherapy studies. We considered implementing a more intensive/formal counseling approach, but opted against it for multiple reasons: 1) the main test is a pure comparison of varenicline versus placebo, 2) the absence of intensive behavioral treatment is consistent with "real world" clinical practice (physician provision of pharmacotherapy without intensive/formal counseling), and 3) utilizing psychosocial methods that closely parallel prior research improves our ability to compare outcomes with the existing adolescent (17) and adult (23-25) cessation literature.

C3e. Instruments/Measures/Materials***Baseline Screening, Diagnostic, and Motivation/Self-Efficacy/Psychosocial Assessments***

1. **Demographic and Smoking History Questionnaire:** Basic demographics, including age, gender, race, social history, and a detailed smoking history will be collected.
2. **Locator Form:** Contact information including address, phone, email, etc. will be collected. Contact information will be reviewed and updated as necessary throughout the study. The research team will have a Facebook page. Privacy settings will be such that only the research team will be able to see the list of "friends" associated with the account, no one can post on the "wall", and the research team will not post on the walls of any "friends" associated with the account. The research team will use private messages to contact participants through Facebook.
3. **History and Physical Examination:** This will be used to assess for any significant medical conditions that would preclude study participation. The physical examination will include all major systems that may be examined non-intrusively (i.e., excluding breast and genitourinary examination).

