Categorical clinical and demographic variables will be assessed by chi-square tests of independence, while continuous variables will be assessed using Student's *t*-test. The effect of varenicline versus placebo on abstinence at end of treatment will be examined using logistic regression. Models will be computed both unadjusted and adjusted for significant covariates found in the descriptive analysis. For these efficacy analyses, 7-day point prevalence abstinence will be defined as having no cigarettes (or other tobacco/nicotine products) for 7 days, confirmed by urine cotinine level ≤ 50 ng/mL. All randomized participants will be included in the analyses (intent-to-treat approach), and participants will be considered non-abstinent at any missed visit.

Safety: Primary Analysis

Similar to adult varenicline phase III studies (23,24), we define any treatment-emergent adverse event any adverse event occurring between treatment initiation and one week following treatment conclusion. Non-inferiority analysis will be utilized to compare adverse event rates between varenicline and placebo groups (84). With a type 1 error rate of 5% ($\alpha = 0.05$) and power ($1 - \beta$) of 80%, the proposed total sample size of 166 and an estimated placebo rate of treatment-emergent adverse events of 75% (23) will afford a non-inferiority margin (NIM) of 16.7% for the varenicline adverse event rate. We considered incorporating a larger sample

Pro00014398

size that would afford a smaller NIM. However, even to detect a 12.5% NIM, a total sample size of 376 participants would be necessary. That sample size would not be feasible within the proposed funding period.

Smoking-Related Outcomes: Secondary Analysis

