4.4 Quality Assurance

Accuracy and completeness of the data collected will be ensured by weekly review. A 10% random sample of the primary source document will be crosschecked with the database on a quarterly basis. If inaccuracies exceed 4%, then a second 10% will be randomly chosen for audit. The REDCap system does not accept outliers, illogical response patterns, etc. The PI will have weekly meetings with the research assistants to discuss qualitative comments received during data collection and any problems in data collection or entry. The statistician will periodically examine the database to look for irregularities. Initial data analyses will examine distributions of variable scores and comparability of baseline characteristics across conditions in case analyses need to be adjusted for these. Confidentiality protections are outlined above.

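### The primary logistic model is fitted twice, once with covariates chosen from the trial data, and the plan does not say which model or which test decides Hypothesis 1

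*Combined protocol and SAP*

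**What the plan says.** Section C3f (Efficacy: Primary Analysis) examines Week 12 abstinence by logistic regression and then says: "Models will be computed both unadjusted and adjusted for significant covariates found in the descriptive analysis". The descriptive analysis consists of chi-square tests and t-tests. The section gives no list of variables and no significance threshold. It does not say whether those tests compare the arms or compare abstainers with non-abstainers.

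Four other places bear on the choice:

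- C3c (Intake and Randomization): "We will stratify by the prognostic covariates age (14-17 versus 18-21) and baseline smoking level". Further variables were left out of the stratification because the authors "judged that these could be adequately explored as covariates during efficacy analyses (see Section C3f").
- C3d (Psychosocial Intervention), explaining why intensive counselling was not used: "the main test is a pure comparison of varenicline versus placebo".
- C3f (Sample Size and Power), for 6.25% versus 26.7%: "this would require 51 participants per group using a two-sided Pearson's Chi Square test statistic". The final 83 per group targets an odds ratio of 4.0.
- Section 4.4 (Quality Assurance): initial analyses will examine "comparability of baseline characteristics across conditions in case analyses need to be adjusted for these".

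The age strata are also said to give an "added opportunity to compare outcomes (in exploratory fashion) between younger and older adolescents". That concerns subgroups and says nothing about the primary model. The endpoint, time point, analysis set and missing-visit rule are all fixed.

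**The concern.** There are two candidate primary results and no rule for choosing between them. One of them uses covariates picked by significance in the trial's own data, so its content is unknown in advance. C3c calls age and baseline smoking prognostic, yet the adjusted model need not include either. If selection means imbalance between arms, stratified randomisation makes these two factors the least likely to be picked.

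Logistic regression also offers Wald, likelihood-ratio and score tests of the same coefficient, and with few events they can give different verdicts. What is at stake is whether a reader can say beforehand which odds ratio and p-value will decide the trial's only primary efficacy hypothesis.

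**Working it through.** **1. The plan's own sample sizes.** Inputs from C3f: two-sided α 0.05, power 80%, p0 = 0.0625, and p1 = 0.267 or the rate at an odds ratio of 4.0.

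Rate at OR 4.0: odds = 4 × 0.0625/0.9375 = 0.2667, so p1 = 0.2667/1.2667 = 0.2105 (stated as 21.1%).

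n per arm = [1.96 √(2 p̄(1−p̄)) + 0.8416 √(p0(1−p0) + p1(1−p1))]² / (p1−p0)², where p̄ is the mean of p0 and p1.

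- 6.25% vs 26.7%: 50.5, rounded up to 51, as stated.
- 6.25% vs 21.05%: 83.3. The plan has 83, rounding up gives 84, and power at 83 is 79.9%.

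The sizing therefore matches an unadjusted Pearson test.

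**2. Expected abstainers.** Design effect: 83 × 0.0625 + 83 × 0.211 = 5.19 + 17.51 = 22.7. Both arms at 6.25%: 166 × 0.0625 = 10.4.

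**3. The unnamed test, unadjusted model.** With a and b abstainers of n = 83 per arm, add the binomial probabilities of all pairs (a, b) whose statistic exceeds 3.841.

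- Pearson (the score test of this model): (b/n − a/n)² / [2p(1−p)/n], with p = (a+b)/2n.
- Wald: (log OR)² / [1/a + 1/(n−a) + 1/b + 1/(n−b)].
- Likelihood ratio: twice the log-likelihood difference between separate rates and a common rate.

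| Test | Null error, 6.25% in both arms | Power at OR 4.0 |
|---|---|---|
| Pearson/score | 4.3% | 81.8% |
| Wald | 2.4% | 80.1% |
| Likelihood ratio | 6.3% | 82.6% |

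Wald and likelihood ratio disagree in 3.9% of null trials and 2.5% at the design effect. For example, 5/83 against 13/83 gives p = 0.046 (Pearson), 0.054 (Wald) and 0.042 (likelihood ratio). This step needs only the plan's rates and sample size.

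**4. Two models.** The documents give no covariate list, so these simulations rest on assumptions. All use 166 participants, independent normal covariates and entry at p < 0.05.

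*Set A* (6,000 trials per scenario, likelihood ratio): 8 or 20 candidates plus the two strata, half of the candidates prognostic at OR 1.0 to 1.5 per SD, an assumed urn, strata split 50/50, stratum OR 1.5. The even split follows C3b, "we anticipate recruiting similar proportions of younger versus older adolescents", and the cut at a prior-trial median for smoking.

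| Selection by | Models disagree, design effect | Null error if either counts | Unadjusted alone |
|---|---|---|---|
| Imbalance between arms | 1.4–4.2% | 5.6–6.5% | 5.3–5.7% |
| Association with abstinence | 1.8–8.3% | 5.8–7.9% | 5.3–5.7% |

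*Set B* (3,000 trials per setting): 8 covariates, log-OR 0.4 per SD. Null error if either model counts, with the unadjusted model alone in brackets:

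| Common rate, test | Imbalance selection | Outcome selection |
|---|---|---|
| 6.25%, Wald | 2.3% (2.1%) | 3.4% (2.2%) |
| 6.25%, likelihood ratio | 6.5% (6.3%) | 7.8% (6.4%) |
| 14%, Wald | 5.5% (4.9%) | 6.3% (4.5%) |
| 14%, likelihood ratio | 6.6% (5.9%) | 7.2% (5.3%) |

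At OR 4.0 the models disagree in about 3% (imbalance) to 7% (outcome) of trials.

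**5. The strata.** Assumed: stratum OR 1.5 or 2.5, strata split 50/50 or 70/30, 10,000 trials per scenario. At the design effect, unadjusted and strata-adjusted analyses disagree in 1.7–3.4% of trials with the assumed urn, and in 0.4–1.6% with blocked or exactly balanced strata. Power of the Cochran-Mantel-Haenszel (CMH) test without continuity correction, minus Pearson power, is −0.1 to +1.4 points. Null error is 4.6–5.1% for this CMH test and 4.0–5.2% for Pearson.

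The assumed urn leaves about one third of the imbalance variance of simple randomisation. A between-arm rule at 0.05 would then select a given stratifier with probability of about 2[1 − Φ(1.96√3)] = 0.07%.

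**The case against.** The best reply is that the plan already points to the unadjusted result: the sample size uses Pearson, C3d speaks of a pure comparison, and C3c only explores other covariates. Pearson is also the score test of the unadjusted logistic model, so the pieces fit. That is a fair inference, but none of these places designates a model. The Pearson test appears only in the sizing paragraph, the C3d remark concerns counselling, and C3c refers the reader back to C3f.

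Three parts of the reply stand. Naming the unadjusted Pearson test would close the gap, so a stratified test is a preference and not a necessity. Most of the magnitudes rest on assumed covariates and an assumed urn. Part of the excess error by likelihood ratio belongs to that test itself.

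A reader might infer that two candidate analyses push false-positive error towards 1 − 0.95² = 9.75%. That figure assumes independent tests. These two models are highly correlated, and with Wald at a 6.25% common rate the error stays below 5%. A reader might also infer that leaving out the strata is the main fault, or a minor one. Under urn allocation the disagreement ranges for strata (1.7–3.4%), between-arm selection (1.4–4.2%) and choice of test (about 2.5%) overlap, so no ranking is supported.

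**Conclusion.** The point holds as an unfixed decision rule for the primary hypothesis and should be corrected. It is not a sample-size error: 51 is reproduced exactly and 83 to within one participant. The differences between tests are exact at the plan's own rates. The differences between models, roughly 1% to 8% of trials at the design effect, are illustrations under the stated assumptions and not properties of this plan. The documents do not support a claim of serious type I inflation, or of a type I benefit from stratifying.

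**What to change.** In C3f (Efficacy: Primary Analysis), replace both the sentence that names logistic regression and the sentence on unadjusted and adjusted models. Replacing only the second would leave logistic regression in conflict with the deciding test. Suggested text:

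> Hypothesis 1 is decided by one two-sided test at 0.05 of Week 12 cotinine-confirmed abstinence between arms, stratified by the randomisation factors (age 14-17/18-21; baseline smoking <12/12 or more cigarettes per day): the Cochran-Mantel-Haenszel test without continuity correction, which is the score test for treatment within strata. The odds ratio with a 95% profile-likelihood interval is estimated by logistic regression on treatment and the two factors; it is descriptive and may occasionally differ from the test at the 0.05 boundary. The unadjusted comparison (Pearson chi-square, as used for the sample size) is a sensitivity analysis. No covariate in the primary analysis is chosen by a significance test; models with other covariates are exploratory.

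Align the adjustment phrase in Section 4.4. The continuity correction has to be ruled out explicitly: in the step 5 simulations it lowers CMH power from 81.2–83.9% to 73.9–77.1%.

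The stratified test is preferred because it matches the randomisation; the power gain is about one point at most. Naming the unadjusted Pearson test as the sole primary test is an acceptable alternative.

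The cost is wording in two sections. Both factors are already recorded for randomisation, and neither N = 166 nor any visit changes. One residual cost remains: under the assumed urn (6,000 trials per scenario), CMH and the likelihood-ratio test, which corresponds to the profile-likelihood interval, differ in 1.4–1.7% of trials at the design effect and 1.1% under the null. The text therefore says which of them decides.
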